In accordance with ASCO guidelines, participants with no/mild symptoms will be provided with written survivorship resources (a letter that contains a link to the National Cancer Institute booklet "Facing Forward: Life after Cancer Treatment") and will not be randomized (Appendix 20). Participants with either moderate or severe distress (anxiety or depressive symptoms) will be randomized into stepped-care telehealth (tailored to level of symptoms) or EUC. For participants with moderate symptoms (PHQ-9: 8-14; GAD-7: 10-14), low-intensity stepped-care telehealth will consist of a self-guided cognitive behavioral therapy (CBT) workbook to reduce anxiety and depressive symptoms and biweekly (every two weeks) check-in calls from research staff at NCORP components. On the biweekly check-in calls, research staff from NCORP components will provide minimal support and will administer the scripted "Telephone Script/Manual for Low-Intensity Group Check-in Call Form." This form assesses changes in symptom severity during the past two weeks. The site staff person is directed to follow Telehealth crisis protocol, refer to Appendix 21, for participants indicating "thoughts of death or suicidal ideation." Site staff should also follow crisis procedures for any other problems identified during administration of the form where follow-up is needed.

For participants with severe symptoms (PHQ-9: 15-27; GAD-7: 15-21), high intensity stepped-care telehealth will consist of a CBT workbook with accompanying psychotherapy by a Master's- or doctoral-level therapist delivered by telephone. Participants randomized to EUC will receive survivorship resources (Appendix 20) and referral information for local mental health providers.

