## **4. PARTICIPANT SELECTION**

### **4.1 Inclusion Criteria**

- 4.1.1.** Age  $\geq 18$  years
- 4.1.2.** Score  $\geq 10$  on the GAD-7 and/or a score  $\geq 8$  on the PHQ-9, indicating clinically significant anxiety or depressive symptoms, respectively.
- 4.1.3.** Past history of treated (newly diagnosed or recurrent) breast, colorectal, prostate, gynecologic (only uterine and cervical) cancers (Stage I, II, or III) or any stage lymphoma (Hodgkin's or non-Hodgkin's).
- 4.1.4.** 6-60 months post-treatment (surgery, chemotherapy, radiation therapy, and/or maintenance therapies) for cancer. Time frame applies to most recent completion of treatment if participant had a cancer recurrence. It is acceptable to be on hormonal therapies.
- 4.1.5.** Participant resides in California, Georgia, Illinois, Kansas, Michigan, Minnesota, Missouri, New Mexico, North Carolina, North Dakota, South Carolina, Virginia, Tennessee, or Wisconsin.
- 4.1.6.** Study-trained therapist in the state where the participant resides.
- 4.1.7.** Must be able to speak and understand English.
- 4.1.8.** Must have access to a telephone. If a patient does not have access to a phone or has difficulty paying for minutes for a mobile phone, the research team should contact the Wake Forest investigators or site coordinators to arrange for assistance.

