#### **7.3.4. Full Screening**

If a participant meets the eligibility criteria on the pre-screen, the participant will be asked to complete the Abbreviated Verbal Consent for full screening. Once a participant has agreed to the abbreviated verbal consent, emergency contact information will be collected and the PHQ-9 and GAD-7 will be administered. If the participant is eligible based on the scoring of the PHQ-9 and GAD-7, then additional screening questions will be administered.

- The PHQ-9 is a nine-item self-report measure used for screening, diagnosing, monitoring and measuring the severity of depression that incorporates DSM-IV depression diagnostic criteria. A score  $\geq 8$  indicates moderate depressive symptoms, and a score  $\geq 15$  suggests severe depressive symptoms
- The GAD-7 is a seven-item self-report measure that incorporates DSM-IV symptoms for generalized anxiety disorder. A score  $\geq 10$  indicates moderate anxiety symptoms, and a score  $\geq 15$  suggests severe symptoms.

All pre-screening and/or screening steps may be completed in one visit or phone call. If done in person, the anxiety question, PHQ-2, PHQ-9 and GAD-7 are to be interviewer administered, and there should not be any missing data on these forms.

Subjects who agree to the abbreviated verbal consent and do not complete the full screening at this time will be contacted up to 5 more times by the site staff. After 5 contact attempts the subject will be considered lost to follow-up and will be considered a screen fail, unless the subjects re-contacts the site. Site staff will enter any screening information collected in the Telehealth website.

Randomization must happen within 30 days of screening. If more than 30 days has passed, the full screening assessment should be re-administered.

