#### **Interviewer Administered Measures and Chart Review (Appendix 6):**

NCORP component research staff will administer the following forms (see Appendices) by telephone (or in person if participant is in clinic) and enter the data on the study website as the data are collected.

These forms are to be interviewer-administered whether the contact is by telephone or in person.

The PHQ-9 and GAD-7 should have no missing data.

- PHQ-9 (administer only if it has been >30 days since screening to reassess eligibility)
- GAD-7 (administer only if it has been >30 days since screening to reassess eligibility)
- Charlson Comorbidity Index
- Cornell Services Index
- Current Medication Use

Chart Review:

- Initial Cancer Diagnosis and Treatment Form
- Additional Malignancy Diagnosis and Treatment Form
- Cancer Relapse/Recurrence Form

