### 8.2 Secondary Endpoints

#### 8.2.1. Depression and Anxiety Measures

The **PHQ-9** is a self-report measure of DSM-IV symptoms of Major Depressive Disorder. Participants rate how often they have experienced nine symptoms over the past 2 weeks on a scale of 0 (not at all) to 3 (nearly every day). Responses are summed, with higher scores indicating greater depressive symptomatology. It has demonstrated good reliability and validity. The traditional cutoff for the PHQ-9 is a score  $\geq 10$ . However, ASCO guidelines recommend using a score  $\geq 8$ , based on a study of cancer outpatients and a meta-analysis of use of the PHQ-9 for identifying depression in cancer patients.

The **GAD-7** is a self-report measure of DSM-IV symptoms of GAD. Participants rate 7 questions on a scale of 0 (not at all) to 3 (nearly every day); one additional question assesses the interference of these symptoms with functioning. The first 7 questions are summed to create a total score. It has been validated for use in the general population and in primary care. The GAD-7 has demonstrated good sensitivity (89%) and specificity (82%) in identifying GAD diagnoses when using a cut point of 10. It also has good internal consistency (alphas = 0.89-0.92) and test-retest reliability (intraclass correlation = .83).

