### 13.3 Sample Size

The sample size (N=90) is based on goals of estimating retention, recruitment, adherence and accrual rates and effect sizes to inform design of a larger efficacy trial. If the drop-out rate is  $>30\%$ , a larger study may not be feasible. With N=90, we are confident that this rate will be  $\leq 30\%$  when the observed drop-out rate is as large as 22% (upper limit of the one-sided 95% CI is 29.2%). Similarly, the lower limit of a one-sided 95% confidence interval for the recruitment rate can be estimated within 8.2% of the observed rate if we approach at least 100 participants to recruit 90, and the lower limit of a one-sided 95% confidence interval for the adherence can be estimated within 8.7% of the observed rate with N=90. Using the normal approximation to the Poisson, we can estimate the lower limit of the one-sided 95% confidence interval of the accrual rate within approximately 2 people per month if the observed rate is 11 people per month. To compare differences between the groups on changes in the PHQ-9 and GAD-7 scores, we can estimate the intervention effect within  $\pm 0.46$  SD with a sample size of 36/group (stepped-care telehealth, enhanced usual care), allowing 20% dropout of the 45/group randomized. This corresponds to 2.7 points on PHQ-9 and 1.9 points on GAD-7 using SDs from studies of change in the measures of 5.8 and 4.2 points, respectively.

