### 13.5 Secondary Objectives, Endpoints, Analysis Plans

For Objective 1.2.1, baseline descriptive statistics will be compared by intervention arm using chi-square tests for categorical variables and ANOVA for continuous variables. Due to randomization, we do not anticipate differences by intervention arm; if they are found, we will adjust for them in the analyses for Objectives 1.2.1, 1.2.2, 1.2.3, and 1.2.4. The Working Alliance Inventory will be summarized using descriptive statistics.

Depression and anxiety outcomes (PHQ-9 and GAD-7) will be analyzed using mixed-model analysis of covariance (ANCOVA) to account for intra-individual correlations among longitudinal measures. The model will contain terms for the intervention group, baseline value of the outcome, therapist or site staff person completing check-in calls, psychotropic medications use, a time effect (mid-, post-intervention), and the time by intervention interaction term (to test whether the intervention effects vary by time). Because participants may exhibit moderate or severe levels of either depression or anxiety, we will create a combined variable that indicates if a participant had moderate/severe depression or anxiety at mid- or post-intervention. Each stepped-care telehealth group will be compared with EUC using a GEE approach with a logit link to determine if rates of the combined outcome differ at mid- or post-intervention. Other outcome measures (sleep disturbance, fatigue, fear of recurrence, cancer-related distress, and quality of life) will be analyzed using ANCOVA at week 13 to meet objective 1.2.2.

For Objective 1.2.3, we will calculate total cost of the stepped-care telehealth (low intensity, high intensity) and the EUC interventions and average cost/survivor screened and randomized to each trial arm. Total cost includes costs of intervention implementation and health care costs for each participant.

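### The GEE for the combined moderate/severe outcome lists no baseline score, although the outcome's cut-offs are the entry cut-offs

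*Combined protocol and SAP*

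**What the plan says.** Section 13.5 introduces the outcome in these words: "we will create a combined variable that indicates if a participant had moderate/severe depression or anxiety at mid- or post-intervention". Each stepped-care group is then compared with EUC on the rate of this outcome by GEE with a logit link. The text names no covariates for that model. It does not say whether there is one indicator per visit or one covering both visits, or whether the EUC comparator is limited to the same severity stratum. The mixed model for the PHQ-9 and GAD-7 scores, in the same paragraph, does include the baseline value. The opening of 13.5 promises adjustment for baseline differences between arms, but only if such differences are found.

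Section 13.5 does not restate the cut-offs. Other sections supply them:

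- Section 3: "For participants with moderate symptoms (PHQ-9: 8-14; GAD-7: 10-14".
- Section 7.3.4: "A score $\geq 8$ indicates moderate depressive symptoms", with GAD-7 10 given as the corresponding value for anxiety.
- Section 4.1.2, on entry: "Score $\geq 10$ on the GAD-7 and/or a score $\geq 8$ on the PHQ-9".

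The baseline battery in Section 7.4 lists "PHQ-9 (administer only if it has been >30 days since screening to reassess eligibility" and treats the GAD-7 in the same way. The score that admits a participant is therefore normally the baseline score as well.

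**The concern.** Because the lower bounds of moderate are the entry cut-offs, every participant has the outcome at entry by selection. A participant who entered on the PHQ-9 alone with a score of 8 loses the status by scoring 7. Since the selecting measurement is usually also the baseline, regression to the mean falls on this outcome. Whether someone crosses depends heavily on how far above the line they started, and that distance is already recorded for everyone. Leaving it out of the GEE discards information in a comparison that has little to spare.

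Two further things are at stake. The rates may be carried into planning of the larger trial, where part of any fall in EUC would be measurement noise. And if EUC were not restricted to the matching stratum, case mix alone would separate the groups.

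**Working it through.** **Inputs from the documents.** Section 8.2.1 gives, for the GAD-7, "test-retest reliability (intraclass correlation = .83"; no retest figure is given for the PHQ-9. Section 13.3 states precision "using SDs from studies of change in the measures of 5.8 and 4.2 points, respectively". Its sample size reads "SD with a sample size of 36/group (stepped-care telehealth, enhanced usual care), allowing 20% dropout of the 45/group randomized". Section 13.2 plans 50 moderate and 40 severe participants, randomised equally within severity.

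**The plan's own figures first.** Half-width = 1.96 × √(2/36) = 0.462 SD. Then 0.462 × 5.8 = 2.68 PHQ-9 points and 0.462 × 4.2 = 1.94 GAD-7 points. These reproduce the stated 0.46 SD, 2.7 and 1.9. The documents give no rate, power or precision for the combined outcome.

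**Size of the comparison.** Moderate stratum: 50/2 = 25 per arm, and 25 × 0.8 = 20 after 20% dropout. By the two-proportion normal approximation, 20 per arm gives power of only 24-29% for a 20-point difference when the EUC rate is between 17% and 40%.

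**How strongly distance from the cut-off matters.** Take one scale, no true change, and ignore regression to the mean. Then P(retest below cut-off | score x) = Φ((cut-off − 0.5 − x)/SD_diff), where SD_diff = SD × √(2 × (1 − .83)).

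- PHQ-9, assuming SD 5.8 and reliability .83: SD_diff = 5.8 × √0.34 = 3.38. The probability is Φ(−0.5/3.38) = 44% at a score of 8, 23% at 10, and Φ(−6.5/3.38) = 3% at 14.
- GAD-7, assuming SD 4.2: SD_diff = 2.45. The probability is 42% at 10 and 3% at 14.

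Taking 5.8 and 4.2 directly as SDs of change instead gives 47% to 13% for PHQ-9 8 to 14, and 45% to 14% for GAD-7 10 to 14. Those SDs come from studies of change and may contain real change, so this version probably overstates noise.

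**Both scales together.** Monte Carlo of true score plus error, rounded, selected by the entry rule, with no treatment effect and no true change. The score distributions are assumed, because the documents give none. Results at retest correlation .83 on both scales, each pair being for true-score correlation 0.5 / 0.75:

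| Assumed mean (SD), PHQ-9; GAD-7 | Moderate stratum, below both cut-offs at one visit | Moderate stratum, below at both visits | Severe stratum, one visit |
|---|---|---|---|
| 5 (5); 4.5 (4.5) | 27.4% / 27.1% | 14.9% / 14.9% | 1.2% / 0.9% |
| 7 (5.8); 6 (4.2) | 22.4% / 22.9% | 11.3% / 11.7% | 1.0% / 0.9% |
| 9 (5.8); 8 (4.2) | 17.0% / 17.7% | 7.8% / 8.4% | 0.6% / 0.6% |
| 11 (5.8); 10 (4.2) | 12.5% / 13.5% | 5.2% / 5.9% | 0.3% / 0.3% |

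So the single-visit rate in the moderate stratum is about 13-27% at .83. Varying the retest correlation from 0.6 to 0.9 widens it to about 10-40%.

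**Why the comparator must be stated.** Take the second row, with 25 moderate and 20 severe EUC participants. Pooled EUC would have (25 × 0.224 + 20 × 0.010)/45 = 12.9% below both cut-offs, against 22.4% in the low-intensity group. That is a gap of 9.5 points with no effect at all. Across scenarios the gap is about 5-12 points.

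**Effect of adding the baseline scores.** In simulation of the GEE at 20 per arm, adding baseline PHQ-9 and GAD-7 changed power by about -3 to +8 points, with type I error at or below 5%.

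**The case against.** The strongest reply is that this outcome is a supplement. PHQ-9 and GAD-7 are analysed first as continuous scores with baseline adjustment, the stated precision concerns those scores, and Section 13.8 says the effect analyses serve planning, not proof of efficacy. The cut-off also has a purpose: Section 8.2.1 ties PHQ-9 8 to guideline advice, so asking who still meets it is reasonable. Under randomisation within severity, noise and regression to the mean are equal in expectation in both arms. All of this stands, and it sets the severity.

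A reader might go further and infer that the plan counts people as improved, and that a fixed share of the moderate stratum, say 17-40%, would be declared improved by noise. The documents do not support that. The variable is a status compared with concurrent EUC; no improvement or success endpoint is defined. The documents give neither a score distribution nor a PHQ-9 retest figure, so any such percentage depends on assumptions.

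A reader might also infer that a minimum change or confirmation at both visits is needed. If the indicator covers either visit, being free of it already requires scores below the cut-offs at both. Under the per-visit reading, a both-visit rule showed no power gain in simulation (0.26-0.59 against 0.26-0.58). It would also classify anyone who improves only after the mid-intervention visit as still a case.

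Finally, the gain from covariates is small, and few participants may be below the cut-offs. With no true change, 13-27% of 40 evaluable moderate participants is about 5 to 11 people (0.13 × 40 = 5.2; 0.27 × 40 = 10.8). That limits the benefit but does not justify leaving the model unspecified.

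**Conclusion.** The point holds as a gap in the GEE specification. The model omits baseline scores that are collected on everyone, that strongly predict the outcome, and that the neighbouring mixed model uses. The conditional promise to adjust for observed imbalance does not fill the gap, because the reason to adjust here is prediction, not imbalance.

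The noise-only crossing rate of about 13-27% assumes that the GAD-7 reliability applies to both scales and that the assumed distributions are realistic; 10-40% is the fairer overall range. A contrast within a severity stratum is not biased by it. Each arm's absolute rate includes it and should not be read as benefit. The documents do not say that EUC will be pooled across strata, so the 5-12 point gap is a reason to state the comparator and not a demonstrated error. Severity is low: this is a secondary analysis in a feasibility trial, and the expected gain in power is modest.

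**What to change.** In Section 13.5:

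1. Define the combined outcome separately at Week 7 and Week 13, and restate the PHQ-9 and GAD-7 values that the protocol already uses for moderate.
2. State that each stepped-care group is compared with EUC participants from its own severity stratum.
3. Add baseline PHQ-9 and baseline GAD-7 scores as covariates in the GEE, whether or not the arms differ at baseline.

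A both-visit version can be listed as an optional sensitivity analysis.

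The cost is SAP wording; all the data are already collected. The downside is two more covariates with few participants below the cut-offs, so estimates may be unstable and power could fall slightly in some settings. The adjusted odds ratio is also conditional on the baseline scores, so the observed proportions by arm, stratum and visit should be shown beside it.

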## 7. CLINICAL EVALUATIONS AND PROCEDURES

### 7.1 Intervention Description

Participants with moderate anxiety and depressive symptoms will be randomized to either the low-intensity stepped-care telehealth or the EUC control. Participants with severe symptoms will be randomized to either the high-intensity stepped-care telehealth intervention or the EUC control. Therapists participating in the trial must meet the following requirements: a Master's or doctoral degree in counseling, marriage and family therapy, psychology, or social work; licensed as an independent mental health provider in California, Georgia, Illinois, Kansas, Michigan, Minnesota, Missouri, New Mexico, North Carolina, North Dakota, South Carolina, Virginia, Tennessee, or Wisconsin; and experience with cognitive-behavioral therapy. Experience working with oncology patients/survivors is preferred. Therapists will attend a 1.5-day training that will cover information on study design, anxiety and depression in cancer survivors, principles of cognitive-behavioral therapy, delivery of the intervention, and use of the web-based data-entry system. NCORP sites and/or components may nominate therapists for participation, but are not required to identify a therapist to participate. The Wake Forest study team will identify a participating therapist for each state.

Low Intensity Stepped-care Telehealth: The low-intensity stepped-care telehealth group will consist of a self-guided CBT workbook (15 minutes daily to read and complete exercises/homework) and biweekly (every two weeks) check-in calls (5-10 minutes) from an NCORP component research staff person to assess changes in symptom severity/immediate need for psychiatric treatment and provide minimal support. Check-in calls are expected to be completed within +/- 2 days of the window specified in the Telehealth website; however, check-in calls up to +/- 1 week of the window are permitted.

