### **13.2 Randomization/Stratification**

Participants will be stratified by baseline score  $\geq 15$  on the GAD-7 and/or on the PHQ-9, indicating severe anxiety or depressive symptoms, and by whether they qualified for the study by the GAD-7, PHQ-9, or both. Participants with moderate symptoms only (8-14 on the PHQ-9 and  $< 15$  on the GAD-7 or 10-14 on the GAD-7 and  $< 15$  on the PHQ-9) will be randomized to either the low-intensity stepped-care telehealth or to the enhanced usual care (EUC control) with equal probability. Participants with severe symptoms will be randomized to either the high-intensity stepped-care telehealth intervention or the EUC control with equal probability. Participants randomized to the low-intensity stepped care telehealth arm who experience increased symptoms at week seven and now experience severe level of symptomatology will receive the high-intensity intervention (see Section 7.1). Analysis will proceed as intent-to-treat using

their initial stepped-care telehealth assignment; we do not anticipate that many people will change from moderate to severe during the study. We anticipate enrolling 45 patients in the stepped-care telehealth intervention and 45 in the enhanced usual care group. We will enroll 50 participants in the moderate symptom strata, and 40 participants in the severe symptom strata. Block sizes will be chosen randomly to ensure that future assignments cannot be inferred from previous ones.

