### **13.6 Exploratory Objectives, Endpoints, Analysis Plans**

We will perform stratified subgroup analysis of the outcomes in Objectives 1.2.1 and 1.2.2. by gender, age, race/ethnicity, stratification arm (moderate, severe), and psychotropic medication use at baseline to meet Objective 1.3.1 using ANCOVA at week 13. To analyze Objective 1.3.2, we will use a mediation approach to examine whether expectancy ratings mediate the relationship between the intervention and the outcomes of interest (PHQ-9, GAD-7, or the combined outcome) at the intervention mid-point or end. First, we will examine whether the expectancy rating score is a significant predictor of the outcome in the mixed-model analysis of covariance (ANCOVA) model with terms for the expectancy rating score, baseline value of the outcome, therapist or site staff person conducting check-in calls, psychotropic medications use, a time effect (mid-, post-intervention), and the time by intervention expectancy score term (to test whether the expectancy score effects vary by time). Then we will fit the same model with the intervention effect, expectancy rating score, and their interactions with each other and time. If the effect for the mediator is significant in this model and the parameter estimate of the intervention effect is smaller than in the analysis of Objective 1.2.1 it will indicate evidence of mediation.

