### **13.8 Evaluation of Response**

All participants in the study who complete the PHQ-9 and GAD-7 at Week 13 will be evaluable for response to the intervention. In sensitivity analyses, we will evaluate how imputation of these values utilizing either baseline or Week 7 data impact study conclusions. Note that this is a feasibility study and analyses of the intervention effects will be used to plan future studies, not to demonstrate efficacy.

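### The GEE sets each stepped-care intensity group against EUC without naming the matching severity stratum, so read as written it mixes treatment with baseline severity

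*Combined protocol and SAP*

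**What the plan says.** Allocation takes place within severity. Section 7.1 says: "Participants with moderate anxiety and depressive symptoms will be randomized to either the low-intensity stepped-care telehealth or the EUC control". Section 13.2 says of the other stratum: "Participants with severe symptoms will be randomized to either the high-intensity stepped-care telehealth intervention or the EUC control with equal probability". The planned stratum sizes are also in 13.2: "We will enroll 50 participants in the moderate symptom strata, and 40 participants in the severe symptom strata".

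Section 13.5 defines a binary outcome, whether depression or anxiety is at a moderate or severe level at the middle or end of the intervention, and then says: "Each stepped-care telehealth group will be compared with EUC using a GEE approach with a logit link". No EUC subset is named and no covariates are given for this model. The covariate list just before it, which includes the baseline value of the outcome, belongs to the mixed model for the PHQ-9 and GAD-7 scores.

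Three other places bear on the point:

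- Section 13.5 has a conditional rule for baseline imbalance: "Due to randomization, we do not anticipate differences by intervention arm; if they are found, we will adjust for them in the analyses". It covers Objective 1.2.1, to which the GEE belongs.
- Section 13.6 plans, as exploratory work using ANCOVA at Week 13, a "stratified subgroup analysis of the outcomes in Objectives 1.2.1 and 1.2.2. by gender, age, race/ethnicity, stratification arm (moderate, severe") and by baseline psychotropic medication use.
- Section 13.8 says that "analyses of the intervention effects will be used to plan future studies, not to demonstrate efficacy".

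The second stratification factor in 13.2 (qualifying by GAD-7, PHQ-9 or both) appears in none of the listed models.

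**The concern.** Randomisation protects two kinds of comparison here: all stepped care against all EUC, and each intensity group against EUC from its own stratum. It does not protect one intensity group against the whole EUC arm, because the two sides then differ in baseline severity by design.

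The outcome is being at a moderate or severe symptom level at follow-up, which is likely to depend on where a participant started. If severe participants stay symptomatic more often, low intensity will look better than it is and high intensity worse, even with no treatment effect.

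Since the effect analyses are meant for planning, the main harm is a biased planning estimate for each component rather than a false efficacy claim. A real benefit of high intensity could be hidden in this contrast. The only like-for-like estimate left would be the exploratory Week 13 analysis, which does not cover the mid-intervention visit.

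**Working it through.** **The plan's own figure.** Section 13.3 gives ±0.46 SD for 36 per group after 20% dropout from 45. Check: 45 × 0.8 = 36, and 1.96 × √(2/36) = 0.46. With the stated SDs, 0.46 × 5.8 = 2.7 PHQ-9 points and 0.46 × 4.2 = 1.9 GAD-7 points. The figure reproduces, but it is for the pooled comparison. None is given for the intensity-specific contrasts.

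**Group composition.** With 50 moderate and 40 severe participants allocated 1:1 (13.2):

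| Group | Moderate | Severe | % severe |
|---|---|---|---|
| Low intensity | 25 | 0 | 0 |
| High intensity | 0 | 20 | 100 |
| EUC | 25 | 20 | 44 |

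**Bias with no treatment effect.** Let pm and ps be the proportions of moderate and severe participants who are still symptomatic. The documents give neither, so the values below are assumed.

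- EUC rate = (25·pm + 20·ps)/45
- Odds ratio = odds(pm) or odds(ps), divided by odds(EUC rate)

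For 50%/80%, the EUC rate is (12.5 + 16)/45 = 0.633, with odds 1.727. Low intensity: 1/1.727 = 0.58. High intensity: 4/1.727 = 2.32.

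Rejection rates (nominal two-sided 5%) come from exact enumeration at one time point after 20% dropout: 20 low or 16 high against 36 EUC (20 moderate, 16 severe). The first figure is the pooled two-proportion z-test. The second is a Wald test of the log odds ratio, with zero-cell tables counted as non-rejections.

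| pm / ps | EUC rate | OR low | OR high | Rejection, low (z; Wald) | Rejection, high (z; Wald) |
|---|---|---|---|---|---|
| 50/50 | 0.500 | 1.00 | 1.00 | 5.2%; 5.1% | 5.7%; 4.3% |
| 50/60 | 0.544 | 0.84 | 1.26 | 6.3%; 6.2% | 6.7%; 5.6% |
| 50/70 | 0.589 | 0.70 | 1.63 | 9.8%; 9.7% | 10.6%; 8.7% |
| 50/80 | 0.633 | 0.58 | 2.32 | 16.0%; 16.0% | 19.4%; 12.7% |
| 60/90 | 0.733 | 0.55 | 3.27 | 17.8%; 17.8% | 22.9%; 4.4% |

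**Masking.** At 50%/80%, suppose high intensity lowers the severe rate from 80% to 65%. Against severe EUC the odds ratio is (0.65/0.35)/(0.80/0.20) = 0.46. Against all EUC it is (0.65/0.35)/(0.633/0.367) = 1.08, a difference of +1.7 points. The benefit disappears.

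**Does the conditional adjustment rule repair this?** It depends on what an arm is.

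- Three groups (severe: 0/25, 20/20, 20/45): chi-square = 45.0 on 2 df, p = 1.7 × 10⁻¹⁰. Severity is always flagged.
- Two pooled arms (20/45 vs 20/45): chi-square = 0, p = 1. Severity is never flagged.

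**Effect of the remedy.** A logit model with low, high and severity indicators, fitted to the 50%/80% no-effect cells, returns odds ratios of 1.00 and 1.00. Without the severity term it returns 0.58 and 2.32.

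**Precision after the remedy.** The comparisons become 20 vs 20 and 16 vs 16 after dropout.

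- Continuous scores: 1.96 × √(2/20) = 0.62 SD and 1.96 × √(2/16) = 0.69 SD.
- Binary outcome at 50%/80%: 1.96 × √(2 × 0.25/20) = 31 points and 1.96 × √(2 × 0.16/16) = 28 points, against about 27 and 25 points versus all EUC.

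**The case against.** The strongest reply is that 13.5 is silent rather than wrong. Sections 7.1 and 13.2 already define each group's randomised control, and EUC can be read that way. The adjustment rule also covers this objective, and elsewhere the text treats low intensity, high intensity and EUC as separate arms. On that reading severity would be flagged and adjusted for.

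This stands as a plausible intention, but it is not settled. The same rule says no differences are expected, which cannot be true of three groups that differ in severity by design, and 13.2 and 13.3 describe two groups of 45. The validity of the contrast should not rest on which reading the analyst picks.

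Other points have force:

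- The high-intensity rejection rate depends on the test. At 60%/90% it is 22.9% by the z-test but 4.4% by Wald. Neither is a GEE over two visits, so the rejection rates are only a guide. The odds-ratio bias does not depend on the test.
- If severity matters little, restriction costs more than it gains. At 50%/60% the root mean squared error of the risk difference is 0.146 (low) and 0.158 (high) against all EUC, and 0.158 and 0.173 against same-stratum EUC. From 50%/70% upward, restriction is better for both.
- The mixed model already adjusts for the baseline value of its outcome. Leaving the strata out of the pooled comparison does not confound it; it affects precision and standard errors and, in a logit model, the size of the odds ratio, because odds ratios are non-collapsible.
- This is one secondary analysis in a feasibility study, and 13.6 has a like-for-like analysis at Week 13. That analysis is exploratory, uses ANCOVA and does not amend the GEE.

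**Conclusion.** The concern holds for the text as written. The two intensity-specific GEE contrasts compare groups that are 0% and 100% severe with an EUC arm that is about 44% severe, and nothing in the plan reliably corrects this. The direction is systematic whenever severe participants stay symptomatic more often: low intensity is flattered and high intensity penalised.

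The size rests on assumed outcome rates. The spurious odds ratios run from 0.84 and 1.26 (50%/60%) to 0.55 and 3.27 (60%/90%), and there is no bias if the rates are equal. The calculations assume the planned 25/20/45 split, and for the rejection rates equal 20% dropout and a single time point.

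The pooled stepped-care versus EUC comparison is unaffected by this confounding. If same-stratum EUC was intended, stating so resolves the matter. It should be fixed, because these estimates are meant to inform the larger trial.

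**What to change.** In 13.5, state that low intensity is compared with EUC participants from the moderate stratum and high intensity with EUC participants from the severe stratum. Equivalently, fit arm, severity stratum and their interaction in the GEE. Three group indicators plus one severity term give the same two contrasts at a given visit, because only four group-by-severity cells exist. If effects are reported by visit, let these terms vary with time.

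As a separate and lesser change, pre-specify severity stratum and qualifying measure as terms in the GEE, the mixed-model ANCOVA and the Week 13 ANCOVA. Adjustment for the stratification factors then does not hang on a baseline significance test.

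Report the within-stratum precision beside the estimates. The cost is one or two sentences, using variables already recorded at randomisation, and the wider intervals shown above. Those intervals also tell readers how little 16 to 20 completers per group can say about each component.
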